## **Appendix 14      Opioid Craving Visual Analog Scale (Opioid Craving VAS)**

No craving \_\_\_\_\_ Strongest craving ever  
100 mm scale

## Appendix 15 Injection Site Grading Scale

Injection Site Reactions	None (Grade 0)	Mild (Grade 1)	Moderate (Grade 2)	Severe (Grade 3)	Potentially Life Threatening (Grade 4)
Pain	None	Does not interfere with activity	Repeated use of non-narcotic pain reliever > 24 hours or interferes with activity	Any use of narcotic pain reliever or prevents daily activity	Emergency room (ER) visit or hospitalization
Tenderness	None	Mild discomfort to touch.	Discomfort with movement.	Significant discomfort at rest	ER visit or hospitalization
Erythema/Redness* (quantitative)	None	2.5 – 5 cm	5.1 – 10 cm	> 10 cm	Necrosis or exfoliative dermatitis
Induration **	None	2.5 – 5 cm and does not interfere with activity	5.1 – 10 cm or interferes with activity	> 10 cm or prevents daily activity	Necrosis
Swelling ** (subjective)	None	2.5 – 5 cm and does not interfere with activity	5.1 – 10 cm or interferes with activity	> 10 cm or prevents daily activity	Necrosis

\* In addition to grading the measured local reaction at the greatest single diameter, the measurement should be recorded as a continuous variable.

\*\* Induration/Swelling should be evaluated and graded using the functional scale as well as the actual measurement.

Modified from:

U.S. Department of Health and Human Services, Food and Drug Administration, Center for Biologics Evaluation and Research, September 2007. Guidance for Industry: Toxicity Grading Scale for Healthy Adult and Adolescent Volunteers Enrolled in Preventive Vaccine Clinical Trials. [pdf] Available at:

<http://www.fda.gov/downloads/BiologicsBloodVaccines/GuidanceComplianceRegulatoryInformation/Guidances/Vaccines/ucm091977.pdf>. Accessed 14 April 2015.

## Appendix 16 Injection Site Pain Visual Analog Scale (Injection Site Pain VAS)

How would you rate your injection site pain today?

No \_\_\_\_\_ Pain as bad  
Pain as it could be

Please answer the following question by checking the box with either a “Yes” or “No”:  
Are you currently experiencing any burning or stinging at the injection site?

YES

NO

**Appendix 17 Timeline Followback (TLFB) Interview**

TIMELINE FOLLOWBACK INTERVIEW											Ethanol
Study Day	Date (mm / dd / yyyy)	Opioids	Methadone	Bup	Cocaine	Barbit.	Benzos	Amp/Meth	PCP	Completed By: (initials/date)	
	□□ / □□ / 20□□	 Use  No Use	_____	 Use  No Use							
	□□ / □□ / 20□□	 Use  No Use	_____	 Use  No Use							
	□□ / □□ / 20□□	 Use  No Use	_____	 Use  No Use							
	□□ / □□ / 20□□	 Use  No Use	_____	 Use  No Use							
	□□ / □□ / 20□□	 Use  No Use	_____	 Use  No Use							
	□□ / □□ / 20□□	 Use  No Use	_____	 Use  No Use							
	□□ / □□ / 20□□	 Use  No Use	_____	 Use  No Use							
	□□ / □□ / 20□□	 Use  No Use	_____	 Use  No Use							
	□□ / □□ / 20□□	 Use  No Use	_____	 Use  No Use							

## Appendix 18 Euro QoL EQ-5D-5L Health Questionnaire

[figure not shown]
### EQ-5D-5L Health Questionnaire

Under each heading, please check the ONE box that best describes your health TODAY

MOBILITY	
I have no problems walking	
I have slight problems walking	
I have moderate problems walking	
I have severe problems walking	
I am unable to walk	
SELF-CARE	
I have no problems washing or dressing myself	
I have slight problems washing or dressing myself	
I have moderate problems washing or dressing myself	
I have severe problems washing or dressing myself	
I am unable to wash or dress myself	
USUAL ACTIVITIES (e.g. work, study, housework, family or leisure activities)	
I have no problems doing my usual activities	
I have slight problems doing my usual activities	
I have moderate problems doing my usual activities	
I have severe problems doing my usual activities	
I am unable to do my usual activities	
PAIN/DISCOMFORT	
I have no pain or discomfort	
I have slight pain or discomfort	
I have moderate pain or discomfort	
I have severe pain or discomfort	
I have extreme pain or discomfort	
ANXIETY/DEPRESSION	
I am not anxious or depressed	
I am slightly anxious or depressed	
I am moderately anxious or depressed	
I am severely anxious or depressed	
I am extremely anxious or depressed	

- We would like to know how good or bad your health is TODAY.
- This scale is numbered from 0 to 100.
- 100 means the best health you can imagine.  
0 means the worst health you can imagine.
- Mark an X on the scale to indicate how your health is TODAY.
- Now, please write the number you marked on the scale in the box below.

YOUR HEALTH TODAY =

USA (English) © 2009 EuroQol Group. EQ-5D® is a trade mark of the EuroQol Group  
Herdman M, Gudex C, Lloyd A, Janssen ME, Kind P, Parkin D, Bonsel G, Badin X.  
Development and preliminary testing of the new five-level version of EQ-5D (EQ-5D-5L).  
Quality of Life Research (accepted for publication).

**Appendix 19 Short Form (36) Health Survey v2**

**The SF-36v2™ Health Survey**

**Instructions for Completing the Questionnaire**

Please answer every question. Some questions may look like others, but each one is different. Please take the time to read and answer each question carefully by filling in the bubble that best represents your response.

**EXAMPLE**

**This is for your review.** Do not answer this question. The questionnaire begins with the section *Your Health in General* below.

For each question you will be asked to fill in a bubble in each line:

1. **How strongly do you agree or disagree with each of the following statements?**

	Strongly agree	Agree	Uncertain	Disagree	Strongly disagree
a) I enjoy listening to music.					
b) I enjoy reading magazines.					

Please begin answering the questions now.

**Your Health in General**

1. **In general, would you say your health is:**

Excellent	Very good	Good	Fair	Poor
 1	 2	 3	 4	 5

GH01

2. **Compared to one year ago, how would you rate your health in general now?**

Much better now than one year ago	Somewhat better now than one year ago	About the same as one year ago	Somewhat worse now than one year ago	Much worse now than one year ago
 1	 2	 3	 4	 5

HT

**Please turn the page and continue.**

3. The following questions are about activities you might do during a typical day. Does your health now limit you in these activities? If so, how much?

	Yes, limited a lot	Yes, limited a little	No, not limited at all	
a) Vigorous activities , such as running, lifting heavy objects, participating in strenuous sports	 1	 2	 3	PF01
b) Moderate activities , such as moving a table, pushing a vacuum cleaner, bowling, or playing golf	 1	 2	 3	PF02
c) Lifting or carrying groceries	 1	 2	 3	PF03
d) Climbing several flights of stairs	 1	 2	 3	PF04
e) Climbing one flight of stairs	 1	 2	 3	PF05
f) Bending, kneeling, or stooping	 1	 2	 3	PF06
g) Walking more than a mile	 1	 2	 3	PF07
h) Walking several hundred yards	 1	 2	 3	PF08
i) Walking one hundred yards	 1	 2	 3	PF09
j) Bathing or dressing yourself	 1	 2	 3	PF10

4. During the past 4 weeks, how much of the time have you had any of the following problems with your work or other regular daily activities as a result of your physical health?

	All of the time	Most of the time	Some of the time	A little of the time	None of the time	
a) Cut down on the amount of time you spent on work or other activities	 1	 2	 3	 4	 5	RP01
b) Accomplished less than you would like	 1	 2	 3	 4	 5	RP02
c) Were limited in the kind of work or other activities	 1	 2	 3	 4	 5	RP03
d) Had difficulty performing the work or other activities (for example, it took extra effort)	 1	 2	 3	 4	 5	RP04

5. During the past 4 weeks, how much of the time have you had any of the following problems with your work or other regular daily activities as a result of any emotional problems (such as feeling depressed or anxious)?

	All of the time	Most of the time	Some of the time	A little of the time	None of the time	
a) Cut down on the amount of time you spent on work or other activities	 O 1	 O 2	 O 3	 O 4	 O 5	RE01
b) Accomplished less than you would like	 O 1	 O 2	 O 3	 O 4	 O 5	RE02
c) Did work or other activities less carefully than usual	 O 1	 O 2	 O 3	 O 4	 O 5	RE03

6. During the past 4 weeks, to what extent has your physical health or emotional problems interfered with your normal social activities with family, friends, neighbors, or groups?

Not at all	Slightly	Moderately	Quite a bit	Extremely	
 O 1	 O 2	 O 3	 O 4	 O 5	SF01

7. How much bodily pain have you had during the past 4 weeks?

None	Very mild	Mild	Moderate	Severe	Very severe	
 O 1	 O 2	 O 3	 O 4	 O 5	 O 6	BP01

8. During the past 4 weeks, how much did pain interfere with your normal work (including both work outside the home and housework)?

Not at all	A little bit	Moderately	Quite a bit	Extremely	
 O 1	 O 2	 O 3	 O 4	 O 5	BP02

9. These questions are about how you feel and how things have been with you during the past 4 weeks. For each question, please give the one answer that comes closest to the way you have been feeling. How much of the time during the past 4 weeks...

	All of the time	Most of the time	Some of the time	A little of the time	None of the time	
a) did you feel full of life?	 O 1	 O 2	 O 3	 O 4	 O 5	VT01
b) have you been very nervous?	 O 1	 O 2	 O 3	 O 4	 O 5	MH01
c) have you felt so down in the dumps that nothing could cheer you up?	 O 1	 O 2	 O 3	 O 4	 O 5	MH02
d) have you felt calm and peaceful?	 O 1	 O 2	 O 3	 O 4	 O 5	MH03
e) did you have a lot of energy?	 O 1	 O 2	 O 3	 O 4	 O 5	VT02
f) have you felt downhearted and depressed?	 O 1	 O 2	 O 3	 O 4	 O 5	MH04
g) did you feel worn out?	 O 1	 O 2	 O 3	 O 4	 O 5	VT03
h) have you been happy?	 O 1	 O 2	 O 3	 O 4	 O 5	MH05
i) did you feel tired?	 O 1	 O 2	 O 3	 O 4	 O 5	VT04

10. During the **past 4 weeks**, how much of the time has your **physical health or emotional problems** interfered with your social activities (like visiting friends, relatives, etc.)?

All of the time	Most of the time	Some of the time	A little of the time	None of the time	
 1	 2	 3	 4	 5	SF02

11. How TRUE or FALSE is each of the following statements for you?

	Definitely true	Mostly true	Don't know	Mostly false	Definitely false	
a) I seem to get sick a little easier than other people	 1	 2	 3	 4	 5	GH02
b) I am as healthy as anybody I know	 1	 2	 3	 4	 5	GH03
c) I expect my health to get worse	 1	 2	 3	 4	 5	GH04
d) My health is excellent	 1	 2	 3	 4	 5	GH05

## **Appendix 20 Medication Satisfaction Questionnaire**

Overall, how satisfied are you with your current opioid dependence medication?

- 1 = extremely dissatisfied
- 2 = very dissatisfied
- 3 = somewhat dissatisfied
- 4 = neither satisfied nor dissatisfied
- 5 = somewhat satisfied
- 6 = very satisfied
- 7 = extremely satisfied

## Appendix 21 Health Care Resource Utilization Questionnaire

HEALTH INSURANCE			
Primary Health Insurance (Please check all that apply)	 Commercial (for example, Blue Cross Blue Shield, Aetna, Humana, United, Cigna)   Medicare   Medicaid   Veterans Affairs   Workers compensation   Other insurance   Self-pay / Out of pocket/No insurance		
INPATIENT ADMISSIONS			

 
Please list in the table below all inpatient admissions in the past 30 days. If patient is currently hospitalized, please check the box in the "Ongoing" column.
 
If patient has had no previous hospitalizations in the past 30 days, please check the appropriate box below.
 
			
 No hospitalizations since the last study visit			
	Admission Date (dd / mmm / yyyy)	Discharge Date (dd / mmm / yyyy)	Ongoing?      Type of Admission
1.	__ / __ / ____	__ / __ / ____	 Ongoing?  Medical  Surgical  Psychiatric  Other
2.	__ / __ / ____	__ / __ / ____	 Ongoing?  Medical  Surgical  Psychiatric  Other
3.	__ / __ / ____	__ / __ / ____	 Ongoing?  Medical  Surgical  Psychiatric  Other

EMERGENCY ROOM VISITS	

 
Please list how many times the patient has been to the Emergency Room in the past 30 days.
 
	
Type of Problem	Number of Visits
Substance abuse-related	  visits
Other medical problems	  visits

OUTPATIENT SERVICES	

 
Please list how many times the patient has seen 1 of the following health professionals in the past 30 days. The outpatient services captured on this questionnaire are ones conducted outside the study
 
	
Health Professional	Number of Visits
General practitioner / Internist	  visits
Addiction Medicine Specialist	  visits
Therapist / Counselor	  visits
Other: Specialist	  visits
Other: Non-Specialist	  visits

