On Day 1 of the study (initiation of study drug injections), all subjects will receive a SC injection of 300 mg of buprenorphine in RBP-6000. Subsequent doses of RBP-6000 may be adjusted down to 100 mg and back up to 300 mg based on the medical judgment of the Investigator. After injection of RBP-6000, subjects will not be permitted to receive supplemental SUBOXONE sublingual film during the RBP-6000 treatment period. Subjects who require supplemental SUBOXONE sublingual film or other sublingual buprenorphine pharmacotherapy during the RBP-6000 treatment period will be withdrawn from the study and referred for appropriate treatment.

Subjects will return to the clinic for monthly injection visits (every 28 - 2/+ 4 days) for a total of up to 12 injections for *de novo* subjects or for a total of 6 injections for roll-over subjects. ECG recordings and vital signs will be collected pre and post each SC injection. All ECGs will be interpreted by a central monitoring facility. Subject-reported injection site pain Visual Analog

Scale scores (VAS) will be collected at various times up to 1 hour after each injection. Local injection site grading will be collected at various time points starting immediately after injection and will be evaluated for pain, tenderness, warmth, itching, erythema, inflammation or swelling, and bruising using a 4-point severity scale. At each visit after injections begin, the injection site will be assessed by site staff and will also be evaluated for evidence of attempts to remove the depot.

Subjects will need to return to the clinic weekly for the first 5 weeks and biweekly (i.e., every 2 weeks) until injection 6, and monthly for the rest of the study period for urine drug screens (UDS), Timeline Followback (TLFB) interviews, opioid craving VAS evaluation, COWS and subject reported outcomes (Subjective Opiate Withdrawal Scale [SOWS]). Subjects will continue to receive counseling (manual-guided behavioral therapy) during the study.

Safety assessments will be collected at each visit and will include the following: vital signs, electronic Columbia Suicide Severity Rating Scale (eC-SSRS) responses, ECGs, laboratory tests (hematology, chemistry, urinalysis, and pregnancy test), concomitant medications, and AEs.

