### 6.12.4 Healthcare Resource Utilization (HCRU) Questionnaire

The Healthcare Resource Utilization questionnaire will be completed by the Investigator or designee at the time points indicated in the SOEs ([Appendix 1](#), [Appendix 2](#), [Appendix 3](#), [Appendix 4](#), and [Appendix 5](#)). The HCRU will be used to collect current health insurance status, hospitalizations; residential substance abuse treatment; general practitioner, specialist, and counseling visits; and ED visits ([Appendix 21](#)). It will be administered electronically. The outpatient services captured on this questionnaire are ones conducted outside the study. Visits to the study site for scheduled study visits should not be reported here.

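### The hospital-admissions item on the HCRU form carries two reference periods: its instructions say 30 days, its 'none' box says since the last study visit, which is 7 to 14 days at Injections 2 to 6

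*Protocol*

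**What the plan says.** Appendix 21 has three parts that record use of care, all with a 30-day recall.

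- Admissions: "Please list in the table below all inpatient admissions in the past 30 days". Each listed admission has admission and discharge dates and a type. The next instruction reads "If patient has had no previous hospitalizations in the past 30 days , please check the appropriate box below". The box it points to is labelled "No hospitalizations since the last study visit".
- Emergency room: "Please list how many times the patient has been to the Emergency Room in the past 30 days". A number is entered, without dates.
- Outpatient care: "Please list how many times the patient has seen 1 of the following health professionals in the past 30 days". Again a number without dates.

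Section 6.12.4 says who fills it in and when: "The Healthcare Resource Utilization questionnaire will be completed by the Investigator or designee at the time points indicated in the SOEs". In Appendices 1 to 5 the HCRU row is marked at screening, at every injection visit and at EOS/ET. It is not marked at the clinic visits between injections.

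Section 9.7.2 promises summary scores, descriptive statistics and an analysis of change, and leaves the detail to a stand-alone SAP. Sections 2.3 and 4.3 of the SAP also defer to that document, which is not among those available.

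**The concern.** The instruction and the box it refers to name different periods. At every form where another clinic visit has come between, staff who follow the instruction and staff who follow the label can give different answers for the same patient. The damaging direction is a 'none' tick for a patient who was admitted within the past 30 days but before the latest clinic visit. Such an admission is never listed, so the dates on the form cannot rescue it.

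The undated counts raise a smaller matter. The recall length (30 days) differs from the spacing of the forms (28 days, range 26 to 32), so adding counts across forms would not give use over the treatment period.

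At stake is the accuracy of one of the eight health-economic instruments listed in Section 9.7.2.

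**Working it through.** **Inputs**

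- HCRU days (Appendices 2 to 5): Day 1, then Days 29, 57, 85, 113, 141 and 169, and for *de novo* subjects every 28 days to Day 337.
- Last clinic visit before each of Injections 2 to 6, all without HCRU (Appendices 2 and 3): Days 22, 43, 71, 99 and 127. From Day 141 no clinic visit falls between forms. The next-day telephone contacts are not counted as visits; counting them would shorten the later look-backs from 28 to 27 days and change nothing before that.
- Recall: 30 days (Appendix 21).
- Spacing of injections: 28 - 2 = 26 to 28 + 4 = 32 days, which reproduces the minimum and maximum in Section 5.3. All 12 scheduled intervals from Day 1 to Day 337 equal 28 days.

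**1. What the box label covers**

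Look-back = HCRU day minus preceding clinic day. Recall days outside the label = 30 minus look-back. Days since the previous HCRU form outside the label = 28 minus look-back.

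| Form | Preceding clinic visit | Look-back | Outside label, of 30 | Outside label since previous form, of 28 |
|---|---|---|---|---|
| Injection 2, Day 29 | Day 22 | 7 | 23 | 21 |
| Injection 3, Day 57 | Day 43 | 14 | 16 | 14 |
| Injection 4, Day 85 | Day 71 | 14 | 16 | 14 |
| Injection 5, Day 113 | Day 99 | 14 | 16 | 14 |
| Injection 6, Day 141 | Day 127 | 14 | 16 | 14 |
| Day 169 and later | previous HCRU visit | 28 | 2 | 0 |

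Five of the 12 scheduled post-baseline forms are affected in *de novo* subjects and 5 of 6 in roll-over subjects. On the Day 1 form the preceding visit is Day -1, so label and instruction disagree there too, but that form precedes treatment.

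**2. With visit windows**

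At Injection 2 the look-back runs from 27 - 24 = 3 to 33 - 20 = 13 days. At Injections 3, 5 and 6 it runs from 8 to 22 days (for example 55 - 47 and 61 - 39), and at Injection 4 from 83 - 75 = 8 to 89 - 69 = 20. The label therefore falls short of 30 days by at least 30 - 13 = 17 days at Injection 2 and 30 - 22 = 8 days at Injections 3 to 6.

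**3. An example**

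A patient is admitted on Day 60 and discharged before Day 71. The Day 57 form is too early to record it. The Day 85 form looks back to Day 55, so the instruction requires the admission to be listed. The label asks only about the time since Day 71, so a 'none' tick would be truthful.

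**4. The undated counts, if summed**

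Assume a constant visit rate. The ratio of recall days to calendar days is 30 / interval:

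- 28 days: 30/28 = 1.071, or +7.1%. Over the study this is 12 x 30 = 360 recall days for 336 days (*de novo*), or 6 x 30 = 180 for 168 (roll-over).
- 26 days: 30/26 = 1.154, or +15.4%.
- 32 days: 30/32 = 0.938, or -6.3%. Here 2 days per interval are never asked about.

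Section 6.8 allows a dose to be delayed by up to a week. If added to intervals of 28 to 32 days, this gives 35 to 39 days and leaves 5 to 9 uncovered.

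**The case against.** The strongest answer is that the form's instructions are consistent. Listing and ticking are both tied to 30 days, only the label departs from this, and the form is completed by study staff, not by the patient. That is correct. A reader might infer from the label alone that the form tells staff to tick on a since-last-visit basis, or that admissions are being lost. The documents do not support either: staff who follow the instruction will list the Day 60 admission. What remains is that the label is the statement being affirmed, and it permits the wrong answer.

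A second answer is that hospitalization is an SAE criterion (Section 6.10.9.1), to be reported within 24 hours of discovery (Section 6.10.9.2), so admissions are captured elsewhere. This largely stands, but not fully. Section 6.10.3 excludes surgery planned before enrollment for a known condition from AEs, while Appendix 21 has a surgical admission type.

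A reader might also infer that emergency-room and outpatient visits are double-counted and use is biased upward. That would need counts to be added across forms, which no available document plans. Each form reported as its own 30-day count double-counts nothing. The sign is not fixed either: it reverses once spacing exceeds 30 days, and the visit window leans towards longer intervals. Even under summation at 28 days, the 12 *de novo* forms share only 11 x 2 = 22 days among themselves; the other 2 of the 24 excess days fall before Day 1.

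Finally, the fixed 30-day recall has a merit: it gives screening and every later form the same reference length, which suits the planned analysis of change. That stands, and it argues against replacing the recall period.

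**Conclusion.** The point holds as a contradiction within one item of a data-collection form. On a literal reading the box label covers 7 of 30 recall days at Injection 2 and 14 of 30 at Injections 3 to 6, leaving 23 and 16 days in which an admission could go unrecorded. From Day 169 the label covers the whole nominal interval since the previous form. These figures assume nominal visit days and that study visit means a clinic visit. How many admissions are affected cannot be estimated: it depends on which line staff followed and on an admission rate that the documents do not give.

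The count issue is conditional: about +7% at nominal spacing, from +15% to -6% if every interval sat at one end of the window, and only if counts are summed at a constant visit rate.

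Primary safety and secondary clinical outcomes do not use this form. The consequence is confined to a tertiary objective, and the correction is desirable rather than critical.

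**What to change.** 1. Appendix 21: relabel the box so that it refers to hospitalizations "in the past 30 days", matching the instruction above it. Leave the 30-day recall as it is. The cost is one label on an electronic form; forms completed before the change keep the old label.
2. Forms already collected: compare 'none' ticks at Injections 2 to 6 with SAE records of hospitalization over the same 30 days and query mismatches. State in the health-economics SAP that surgical admissions planned before enrollment may be absent from the SAE data, so the check is incomplete. The cost is one listing and some queries.
3. Health-economics SAP: report emergency-room and outpatient use as a rate per 30 recall days and not as a sum over visits. The cost is one derivation.

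Changing the look-back to the time since the previous HCRU form would also remove overlaps and gaps, but windows would then vary in length and no longer match screening. It is not needed to resolve the contradiction.
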